We will meet with each adolescent online for 1 hour to collect further information using an intake assessment form (see the attached "Intake assessment form"). The form will assess headache history and coping responses. The research team will combine the information gathered in phase 1 and phase 2 to create a case conceptualisation. We will also create some brief goals for treatment and will identify key target processes (e.g., psychological coping responses, such as learning what to do during a headache episode) for the personalised intervention. We will collaboratively select 2-3 most personally relevant items from the previously completed PBAT questionnaire (in phase 1), which will form part of further data collection. These questionnaire items will be those deemed to be most relevant to the adolescents' presenting headache concerns, and these will guide the focus of the upcoming intervention. Finally, in Phase 2 we will introduce the upcoming data collection schedule which is described in Phase 3 below.

Phase 3: baseline data.

Participants will begin the Ecological Momentary Assessment (EMA), which they will complete 2-3 times per day, on 3- 4 days per week. The participants will be sent completion prompts via the mPath app. The questionnaires will take up to 2 minutes to complete each time. As per feedback from experts by experience, data collection will be distributed over several days per week to reduce participant burden (e.g., Monday, Wednesday and Friday). At this stage, participants will be completing both primary outcome measures (headache activity, progress towards the personalised goal, and coping with headache), and their personalised PBAT items. Once per week, participants will also receive a questionnaire assessing headache interference and headache-related disability.

Phase 4: intervention and further data gathering.

Each participant will be invited to attend up to 5 weekly online brief therapy sessions, lasting 30 minutes each, to work on the specific target processes identified in Phase 2. The personalised interventions will be drawn from already known evidence-based CBT-based treatments for headache

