management. Clinical supervision during this treatment phase will be provided by the lead project supervisor who holds extensive clinical and research experience in chronic headaches. Due to the intervention being highly personalised, adherence to a specific treatment protocol will not be measured. Additionally, we will administer a Client Feedback Form at the final session.

Participants will begin interventions at different time points, in line with the Multiple-Baseline SCED Design. This will mean that some participants will spend longer completing Baseline data before they begin the intervention phase. We expect the baseline period to be no longer than 2 weeks at most, ranging from several days to 2 weeks. The multiple baseline design protects validity of research by controlling for the effect of passage of time on the results (Slocum et al., 2022). We aim to randomise participants into multiple baselines, rather than selecting participants, to reduce the risk of researcher bias (Levin and Ferron, 2021).

The data collection schedule will remain the same as in Phase 3 (i.e. on 3 days per week, participants will receive 2-3 prompts to fill out a brief questionnaire, and once per week they will receive a prompt to complete a measure of headache-related disability and interference).

The personalisation will be an ongoing collaborative process. This means that the research team will revise the collected data each week, which will consequently inform each session's focus. Within PBT, the network map is viewed as always changing and therefore is revisited frequently during therapy (Ong et al. 2022). Within our study, we will use the network map as the preliminary case conceptualisation to identify key processes that might be contributing to headache-related disability. Consequently, we will collect weekly EMA data in between intervention sessions, and share this with participants to update the network diagram and to identify the key focus of the subsequent treatment sessions. The PBT network map, along with weekly intensive EMA data collection, during treatment and at follow-up, will help us to create a highly personalised, dynamic psychological intervention. The weekly EMA idiographic data will be reviewed with adolescents and will guide:

- a) Network case formulation
- a) Processes to focus on the personalised intervention
- b) Decision-making on the overall course of treatment.

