Data collection schedule: In line with recommendations arising from 24 EMA studies with adolescents, a “burst design” for data collection may be optimal to reduce participant burden (Heron et al, 2017). Participants will therefore have periods of breaks from data collection during each week. This has also been advised by EBEs who took part in trialling the data collection schedule. Compliance with questionnaire completion will also be measured.

Phase 5: Follow-up.

Following intervention completion, participants will continue completing daily questionnaires for a further 1-2 weeks, as well as weekly measures of headache-related disability and interference.

Study end. At the end of the follow-up period, participants will be contacted by email to inform them of the end of the study and to thank them for their participation. Additionally, we will offer an optional online debrief meeting to each participant.

Sample recruitment

The sample will be recruited from a specialist paediatric NHS service (initial discussions are currently ongoing). Clinical staff will identify participants by screening adolescents against the criteria and seeking verbal consent to pass their details to the research team to discuss study participation.

We aim to recruit an adolescent sample size of 12 (to allow for sample attrition) ranging in ages 12-18. We are aiming for a final sample of $n=6$ (i.e. number of participants who complete the study). This sample size is in line with other previous SCED studies with adolescents (e.g., Cawthorne et al., 2022; Sukhodolsky et al., 2013).

Table 1.

Inclusion and exclusion criteria for the study:

Inclusion	Exclusion

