
 - Adolescents aged 12-18. - Recurrent headaches occurring for 3 months or more, ideally (but not necessary)-diagnosed by a paediatric Neurologist (diagnosis of any idiopathic headache, using the International Classification of Headache Disorders criteria (ICHD-3 beta version). - The headache should be deemed to be resulting from a primary headache disorder as opposed to a secondary symptom of another health condition. - Currently not receiving psychological support elsewhere or have prior accengagement with psychological support for or due to headache for the past 6 months prior to screening. - Reporting PedMIDAS score of greater than 10 points (indicating at least minimal disability) - Adolescent and their caregiver fluent in speaking and writing in English - Frequent access to a smartphone and access to the internet whether public (e.g., library) or private (e.g., home, personal) 	
 - Presence, history or suspicion of secondary headache disorder- - PedMIDAS of greater than 140 points (indicating excessive disability and need for multisystemic therapies). - Adolescent and their carer not fluent in speaking and writing in English. - Diagnosis of pervasive developmental disorder or serious mental condition (eg, psychosis, active suicide thoughts) as determined by the referral (either the parent/carer or the medical professional) - Adolescents living in families in distress (e.g., a family member experiencing another illness, mental health problem or psychosocial issues) - Limited access to a smartphone device with consistent internet connection. - Receiving psychological support elsewhere or have a prior engagement with psychological support for headaches up to 6 months prior to screening.

Assessment procedures

Demographics and clinical characteristics

HeadFlex study

Project proposal, Royal Holloway University of London V3

Version and date: V3, September 2024

IRAS project number: 340890

PI: [name], C.Psychol (Clinical & Health) Royal Holloway, University of London

Demographic information will be collected using Qualtrics between Phase 1 and 2. This will include the adolescent's age, gender, cultural background, headache diagnosis, headache profile (e.g., frequency, intensity, severity), and medication use.

Measures

Primary outcome measures

The primary outcome measures will be a series of Visual Analogue Scale (0-100) items that measure the following:

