1. Perceived progress in a personally defined goal (1 item)
2. Perceived progress in ability to cope with headache (1 item)
3. Headache activity (frequency, duration, intensity and interference) (4 items)

Secondary outcome measures

Participants will respond once per week in a series of standardised measures, using a total of 2 questionnaires as outlined below.

1. Headache interference. The Patient Reported Outcomes Measurement Information System (PROMIS) Paediatric Pain Interference (PPI) Item Bank- 10 items (Varni et al. 2010) measures the daily interference of pain on physical, psychological, and social functioning. Higher scores indicate greater pain interference in the child's life. This is a unidimensional item bank (Varni et al., 2010), derived from a larger PROMIS item bank which has an overall good internal consistency (Cronbach's alpha= 0.98) (Cunningham et al. 2017) and convergent validity shown by significant correlations with other similar scales. The PPI scale has been validated in paediatric chronic pain samples (Ceniza-Bordallo et al., 2022).

2. Measure of headache-related disability. Headache-related disability will be measured using the Paediatric Migraine Disability Assessment Scale (PedMIDAS) (Hershey et al. 2001), which is a 6-item

questionnaire measuring the frequency of disruption to daily activities caused by headaches. This measure has been used in studies measuring headache related disability after pharmacological interventions (Powers et al., 2021). The PedMIDAS has been shown to have internal consistency (Cronbach's alpha 0.80) and validity in measuring headache-related disability (Hershey et al. 2001).

Other measures

Additionally, we will administer a Client Feedback Form at the final intervention session, based on Sekhon et al.'s (2018) theoretical framework of acceptability (TFA) for health interventions. This includes six items, rated on a 5-point Likert scale: affective attitude, burden, perceived effectiveness, intervention coherence, self-efficacy, and opportunity/ costs.

Statistical analyses

To address the first research question, we will analyse the weekly standardised data to assess change in disability (PedMIDAS) and headache interference (PROMIS) assessing reliable change (RC) and clinically significant change (CSC), using Jacobsen & Traux's formula (1991). (Scores will be compared against a calculated reliable change index, to indicate whether the level of change is statistically significant).

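### PedMIDAS is scheduled weekly, but its own eligibility limit implies a look-back of at least about 24 days, so early treatment scores still count pre-treatment days

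*Protocol*

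**What the plan says.** Under Secondary outcome measures, the protocol introduces PedMIDAS as a scale of six items, a "questionnaire measuring the frequency of disruption to daily activities caused by headaches", with a Cronbach's alpha of 0.80. Table 1 uses the same scale for eligibility. The inclusion side asks for "Reporting PedMIDAS score of greater than 10 points (indicating at least minimal disability", and the exclusion side lists "PedMIDAS of greater than 140 points (indicating excessive disability and need for multisystemic therapies".

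The scale is scheduled weekly in every measured phase:
- Phase 3 (baseline): "Once per week, participants will also receive a questionnaire assessing headache interference and headache-related disability".
- Phase 4 (intervention): "once per week they will receive a prompt to complete a measure of headache-related disability and interference".
- Phase 5 (follow-up): "participants will continue completing daily questionnaires for a further 1-2 weeks, as well as weekly measures of headache-related disability and interference".

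Statistical analyses gives these scores their role: "To address the first research question, we will analyse the weekly standardised data to assess change in disability (PedMIDAS) and headache interference (PROMIS", by means of reliable change and clinically significant change. Nowhere does the protocol state a recall period for PedMIDAS, a one-week adaptation or a rescaling.

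**The concern.** A weekly form is useful for tracking change if each score describes roughly the week just past. The exclusion limit of 140 suggests that PedMIDAS does not. If six frequency items can sum to more than 140, the form must look back well beyond seven days. A score collected early in treatment then still counts days before treatment began, so it understates any real change.

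The alternative is that a one-week version is intended but not declared. In that case the reliability quoted for the standard form does not carry over to it without support.

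PedMIDAS is the only measure named for disability in research question (a), and about six completers are expected. One or two misclassified participants would therefore alter the answer. A recall period cannot be corrected once the data are collected.

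**Working it through.** **Inputs from the protocol.** Six items counting frequency of disruption (Secondary outcome measures). Exclusion above 140 points (Table 1). Weekly administration (Phases 3 to 5). Baseline of several days to at most 2 weeks, and up to five weekly sessions (Phases 3 and 4). Follow-up of 1-2 weeks (Phase 5). Alpha 0.80 (Secondary outcome measures).

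**Assumption.** Each item counts at most c disruptions per day, with c = 1 as the base case. An exclusion limit has a purpose only if scores above it can occur.

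**Step 1: look-back implied by the limit.** Maximum score = 6 x c x W, where W is the window in days.
- With W = 7 and c = 1: 6 x 7 = 42, far below 140.
- Smallest W for a score of 141: 141/(6 x 1) = 23.5, so 24 days.
- With c = 2: 141/12 = 11.75, so 12 days. With c = 3: 141/18 = 7.8, so 8 days.
- Fitting 141 into 7 days needs 141/42 = 3.4 counts per item per day.

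The look-back therefore exceeds a week for any c up to 3.

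**Step 2: pre-treatment share of a treatment score.** At day d after session 1 the share is max(0, W - d)/W.

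| W (days) | day 7 | day 14 | day 21 | day 28 | day 35 |
|---|---|---|---|---|---|
| 12 (c = 2) | 42% | 0% | 0% | 0% | 0% |
| 24 (c = 1, minimum) | 71% | 42% | 12.5% | 0% | 0% |
| 42 (assumed) | 83% | 67% | 50% | 33% | 17% |
| 60 (assumed) | 88% | 77% | 65% | 53% | 42% |

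For W = 24 the entries are 17/24, 10/24 and 3/24.

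**Step 3: baseline scores.** Baseline lasts at most 14 days. With W of at least 24, every baseline score also covers days before Phase 3.

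**Step 4: a longer window, as an assumption.** Take W = 13 weeks = 91 days, day 35 as the end of week 5 and day 49 as the 2-week follow-up. The share of the window after session 1 is 35/91 = 38% and 49/91 = 54%.

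**Step 5: the reliable-change threshold.** Assuming that the quoted alpha is the reliability used, the threshold is 1.96 x SD x sqrt(2 x (1 - 0.80)) = 1.24 x SD. The protocol gives no SD. For an assumed SD of 20 to 40 the threshold is 24.8 to 49.6 points.

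**Step 6: illustration.** A participant with a constant daily rate scores 60 and remits completely at session 1. The observed fall at day d is 60 x min(d, W)/W.
- W = 24, day 35: the fall is 60, above the whole threshold range.
- W = 91, day 35: 60 x 35/91 = 23, below the whole range.
- W = 91, day 49: 60 x 49/91 = 32, above the threshold at SD 20 and below it at SD 40.
- Break-even at day 35: W = 60 x 35/24.8 = 85 days at SD 20, and 60 x 35/49.6 = 42 days at SD 40.

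**The case against.** The strongest reply concerns the consequences, and much of it stands.

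- **Missed responders.** A reader might infer that a fully effective treatment would be classed as no reliable change. The documents do not support that. They establish only the lower bound of about 24 days, and at that bound an end-of-treatment or follow-up score contains no pre-treatment days. The missed responder in Step 6 needs a longer window and an SD that the protocol does not give.
- **Overlapping scores.** At 24 days, adjacent weekly scores share 17/24 = 71% of their days, and a reader might infer that this invalidates the analysis. Comparing scores with a reliable change index does not require independent adjacent weeks. Tau-U and the lagged regression, where serial dependence matters, are not assigned to PedMIDAS.
- **Cut-offs.** A reader might also infer that the limits of 10 and 140 fail once the form is weekly. They are eligibility criteria, and nothing says they are applied to weekly scores.
- **Importance.** PedMIDAS is a secondary measure in a small pilot. Question (a) also rests on PROMIS interference, to which this argument does not extend. Dilution would tend to hide benefit, not create it.

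Which weekly scores are compared may be settled in an analysis plan that is not shown. What no analysis plan can settle is the wording of the form already given to participants. The mismatch between weekly use and a scale that must look back further than a week remains.

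**Conclusion.** The point holds at moderate severity. On the protocol's own figures, PedMIDAS as described cannot have a one-week window unless each item is counted about 3.4 times a day. It is nevertheless given weekly and analysed for reliable change. At the 24-day minimum, the scores of roughly the first three treatment weeks mix phases, with 71%, 42% and 12.5% pre-treatment days, and every baseline score reaches back before Phase 3.

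This rests on one assumption, that items count about one disruption per day. The direction survives up to three counts per day, but at two counts only the first treatment week is affected.

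Whether end-of-treatment and follow-up scores are also diluted depends on a recall period that the protocol does not state. At an assumed 13 weeks, only 38% of the week-5 window and 54% of the 2-week follow-up window fall after session 1, and true change could then fall below 1.24 x SD. That is a conditional risk, not an established one.

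**What to change.** 1. State the PedMIDAS recall period in the measures section.
2. Keep the standard form for eligibility, as now. Do not classify reliable or clinically significant change from any treatment or follow-up score whose window includes pre-treatment days. Compare the pre-treatment score with the last follow-up score only if the latter's window lies wholly after treatment start, and otherwise report it descriptively. With five weeks of treatment, this requires a recall period of at most 35 + 7 = 42 days for a 1-week follow-up, or 35 + 14 = 49 days for a 2-week follow-up. It must be shorter for anyone with fewer sessions.
3. For the weekly series, choose one option and say so. Either use a declared past-7-days version (range 0-42 at one count per item per day), reported descriptively and without the published reliability or cut-offs. Or drop PedMIDAS from the weekly set and rest weekly change for question (a) on PROMIS interference and the momentary interference item.

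The cost is a reworded stem in the survey tool and a paragraph in the protocol. The real downside is that the protocol gives no reliability for a past-week version, so no reliable-change classification can be made from it. With the second option, the weekly evidence for question (a) covers interference and not disability.

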A distinct aspect of PBT intervention is ongoing data collection, using methods such as Ecological Momentary Assessment (EMA). Using EMA, we will repeatedly sample symptoms, coping with headache responses, and relevant pain-related behaviours. EMA collects data that captures frequent momentary information from adolescents in the context of their lives, longitudinally (Hedeker et al., 2012). It also helps adolescents increase self-awareness, insight, and self-management of their

headache difficulties (Folkersma et al. 2021). In this study, we will use EMA to collect weekly data, which will inform progress tracking and allow personalised treatment trajectory.

Aim of the project and research question

The objective of this project is to construct idiographic case conceptualisations and deliver brief personalised interventions, guided by weekly data that will inform the course of the intervention. This study will focus on both the pilot efficacy and process of change examination of a highly personalised intervention, collecting baseline, weekly, post-intervention and follow-up data.

Our research questions are:

(a) Is a highly personalised intervention with weekly feedback provision effective in lowering headache disability and improving headache interference?

(b) Does a personalised intervention lead to changes in clinically targeted psychological processes, personalised goals and headache activity (outcomes)?

Plan of investigation

Design

This is a single-case experimental design (SCED) study, with concurrent multiple baselines within-subjects. We will use an AB design, where baseline (A) will always precede the intervention (B) phase for each participant. This design allows participants to act as their own control (Krasny-Pacini & Evans, 2018), whilst also maintaining experimental control. We will follow the SCRIBE statement (Tate et al., 2016) to guide the reporting of this SCED design.

Each participant will partake in a baseline data collection, between 1 to 2 weeks before we deliver the intervention. Participants will not be able to begin any psychological intervention for headaches during the study. Below, we present all the phases of the study.

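### The protocol gives two lower limits for the baseline and two EMA densities, so a baseline shorter than a week could yield few observations and no PROMIS score before treatment

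*Protocol*

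**What the plan says.** **Baseline length.** The Design section of the protocol states: "Each participant will partake in a baseline data collection, between 1 to 2 weeks before we deliver the intervention". The Phase 4 section, explaining the staggered starts, states: "We expect the baseline period to be no longer than 2 weeks at most, ranging from several days to 2 weeks". The upper limits agree and the lower limits do not. The same Phase 4 paragraph says the team aims to allocate participants to baseline lengths at random.

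**EMA density.** Phase 3 describes assessments "which they will complete 2-3 times per day, on 3- 4 days per week", with the days spread out: "data collection will be distributed over several days per week to reduce participant burden (e.g., Monday, Wednesday and Friday". Phase 4 says: "The data collection schedule will remain the same as in Phase 3 (i.e. on 3 days per week, participants will receive 2-3 prompts". Phase 5 says "participants will continue completing daily questionnaires for a further 1-2 weeks", directly after a paragraph promising breaks from data collection within each week.

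**When outcomes start.** Phase 1 collects the PBAT only. Phase 2 is the personalisation meeting: "We will also create some brief goals for treatment and will identify key target processes". The VAS outcomes start in Phase 3: "At this stage, participants will be completing both primary outcome measures (headache activity, progress towards the personalised goal, and coping with headache". The weekly PROMIS interference and PedMIDAS questionnaires also start in Phase 3. Separately, Table 1 requires a PedMIDAS score above 10 for entry and excludes scores above 140.

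**Use in analysis.** The Statistical analyses section answers research question (a) by reliable and clinically significant change on the weekly PedMIDAS and PROMIS scores. It answers question (b) by visual analysis and Tau-U on the repeated series, supplemented by lagged regression models. No minimum number of baseline observations is stated.

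**The concern.** This is an AB design in which participants are their own controls, so phase A supplies the whole comparison. With baseline length to be randomised, someone is meant to receive the shortest one, and the protocol gives two answers to how short that may be.

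Under the looser answer, two things can fail. The weekly form may never fall inside the baseline, which leaves no PROMIS score to subtract from. And the EMA series may rest on one or two days, too few to judge baseline trend or variability, which the planned visual analysis sets out to do. Only 6 completers are expected, so each unusable baseline removes about one sixth (1/6 = 17%) of the evidence. A baseline observation that was never collected cannot be recovered in the analysis.

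**Working it through.** The protocol gives no count of baseline observations, so there is no stated figure to reproduce. The counts below follow from its schedule.

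**Inputs from the protocol:** 2 to 3 prompts per EMA day; 3 or 4 EMA days a week; Monday/Wednesday/Friday as the example spacing; one weekly questionnaire; a baseline of 1 to 2 weeks (Design) or several days to 2 weeks (Phase 4).

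**Assumptions:** several days means 3 to 6 days; the weekly form goes out on one fixed weekday; every starting weekday is equally likely.

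**Prompts.** For a baseline of L consecutive days, count the EMA days in the window for each of the 7 starting weekdays. Minimum prompts = 2 × the fewest EMA days; maximum = 3 × the most.

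**Weekly form.** A window of L < 7 days misses a given weekday for 7 − L of the 7 starting days, so the share missed is (7 − L)/7.

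| Baseline length | EMA days (Mon/Wed/Fri) | Prompts | Weekly form missed |
|---|---|---|---|
| 3 days | 1–2 | 2–6 | 4/7 = 57% |
| 4 days | 1–2 | 2–6 | 3/7 = 43% |
| 5 days | 2–3 | 4–9 | 2/7 = 29% |
| 6 days | 2–3 | 4–9 | 1/7 = 14% |
| 7 days | 3 | 6–9 | 0% |
| 14 days | 6 | 12–18 | 0% (2 forms) |

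With 4 EMA days a week (two spacings tried), the minimum is 2 prompts at 3 days, 4 prompts at 4 or 5 days, and 6 prompts at 6 days. One week gives 4 × 2 to 4 × 3 = 8–12 prompts, and two weeks give 16–24.

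**Comparison with phase B.** Five weekly sessions at the Phase 4 density give 5 × 3 × 2 to 5 × 3 × 3 = 30–45 prompts. At 4 days a week the upper end is 5 × 4 × 3 = 60.

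**Follow-up.** Read literally, daily means 7 × 2 to 14 × 3 = 14–42 prompts. On the Phase 3 schedule it means 1 × 3 × 2 to 2 × 4 × 3 = 6–24.

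**Consequence for reliable change.** The index needs a pre-treatment and a later score on the same scale. PROMIS is first given in Phase 3, so a missed form means there is no pre-treatment value at all. PedMIDAS has an eligibility value, whose role as baseline is not stated.

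**The case against.** The worst case is not a protocol figure. Two prompts requires several days to mean 3 or 4 days, a single EMA day in the window, and the minimum number of prompts that day. Missing the weekly form requires a baseline under 7 days and a form tied to a weekday outside it. The protocol fixes no weekday, and the form could simply be sent on the first day of Phase 3. Under the Design section's floor neither problem arises. All of this stands, and it is why the counts are conditional. It does not remove the conflict that makes the short case possible.

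A reader might infer four stronger points, which the protocol does not support:

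- *Participants could lack any pre-treatment PedMIDAS.* Table 1 makes PedMIDAS an eligibility measure, so a score exists. Only PROMIS could be missing altogether.
- *Follow-up really is sampled every day.* The sentence says participants continue, follows a paragraph on breaks within each week, and contrasts these forms with the weekly measures. Loose wording is the more natural reading.
- *Unequal density biases the phase effect.* The outcomes are 0–100 ratings, not counts summed over prompts, and Tau-U measures overlap. Three days rather than four mainly changes precision. Bias in the frequency or duration items would depend on their recall window, which is not given.
- *Baseline is invalid because outcomes start after the Phase 2 meeting.* The treatment is defined as the weekly sessions. The goal item and the selected PBAT items cannot exist before Phase 2. Any benefit from the meeting would tend to shrink the A–B contrast. Starting the other VAS items earlier is a choice to weigh against burden: about 2 minutes added to a 3–4 minute Phase 1 questionnaire is 50–67% more.

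**Conclusion.** The concern holds for the lower limit of the baseline and for the EMA density. The Design and Phase 4 sections disagree on whether a baseline may be shorter than a week. Phases 3 and 4 disagree on 3–4 versus 3 days while claiming to be the same, and the Phase 5 wording needs clarifying.

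If several days means 3 to 6 days on a Monday/Wednesday/Friday schedule, the baseline holds 2 to 9 prompts, and a fixed-weekday form is missed for 57% down to 14% of starting weekdays. With a one-week floor the schedule supplies at least 6 prompts and 1 weekly form, before any non-completion.

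The firm consequence is limited to reliable change in interference, which cannot be computed for a participant who misses the form, and to weak evidence on baseline trend and variability. For PedMIDAS the gap is only that the protocol does not say whether the eligibility score may serve as baseline.

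**What to change.** 1. Reconcile the Design and Phase 4 sections so that every randomised baseline lasts at least the 1 week that the Design section already states.
2. State one EMA density for Phases 3, 4 and 5, and replace or define the word daily in Phase 5.
3. Require at least one completed PROMIS and one completed PedMIDAS in Phase 3 before session 1, for example by sending the weekly form at the start of Phase 3. Say whether the eligibility PedMIDAS may stand in as a baseline.

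These changes cost protocol wording and app set-up. The upper limit of the baseline stays at 2 weeks, but the one-week floor removes the shortest staggered starts and so narrows the range of baseline lengths to 7–14 days.

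Optional: send the weekly form once in Phase 1, to obtain a score before the personalisation meeting, at the cost of one extra form. Averaging it with the Phase 3 score would cut the standard error of change from √2 = 1.41 to √1.5 = 1.22 standard errors of measurement (13% less). That gain assumes independent errors and pools scores from either side of the meeting, so it should not be the main reason. Starting the headache-activity and coping VAS items in Phase 1 is likewise a design choice to weigh against participant burden.
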